5.1.1.1.3 Decrease in Immunoglobulins

Treatment with ocrelizumab resulted in a decrease in total immunoglobulins (Igs) over 2 years, mainly driven by reduction in IgM, with no observed association with serious infections. The proportion of patients with decrease in Igs below the LLN increased over time and with successive dosing.

5.1.1.1.4 Delayed Return of Peripheral B Cells

Treatment with ocrelizumab leads to rapid depletion of CD19+ B cells in blood by 14 days post-treatment (first timepoint of assessment) as an expected pharmacologic effect. This was sustained throughout the treatment period. The longest follow-up time after the last ocrelizumab infusion from Phase II Study WA21493 in 51 patients indicates that the median time to repletion (returned to baseline/LLN, whichever occurred first) of B cells was 72 weeks (range: 27–175 weeks). Patients with prolonged B-cell depletion should be monitored until their B cells have repleted.

5.1.1.2 Potential Risks

5.1.1.2.1 Hypersensitivity Reactions

No hypersensitivity reactions to ocrelizumab were reported in the controlled clinical trials.

Hypersensitivity may be difficult to distinguish from IRRs in terms of symptoms. A hypersensitivity reaction may present during any infusion, although typically would not present during the first infusion. For subsequent infusions, more severe symptoms than previously experienced, or new severe symptoms, should prompt consideration of a potential hypersensitivity reaction. If a hypersensitivity reaction is suspected during infusion, the infusion must be stopped immediately and permanently. Patients with known IgE-mediated hypersensitivity to ocrelizumab must not be treated.

5.1.1.2.2 Impaired Response to Vaccination

The degree of impairment of B cell-dependent humoral response to neoantigens and polysaccharide antigens and its clinical relevance are currently unknown in patients with MS.

*After treatment with ocrelizumab over 2 years, the proportion of patients with positive antibody titers against *Streptococcus pneumoniae*, mumps, rubella, and varicella were generally similar to the proportions at baseline.*

No data are available on the effects of vaccination in patients receiving ocrelizumab. Physicians should review the immunization status of patients being considered for treatment with ocrelizumab. Patients who require vaccination should complete it at least 6 weeks prior to initiation of ocrelizumab.

The safety of immunization with live or live-attenuated viral vaccines following ocrelizumab therapy has not been studied, and vaccination with live-attenuated or live vaccines is not recommended while B cells are depleted.

Ocrelizumab—Genentech, Inc.

84/Protocol ML29966, Version 4 (Global)

5.1.1.2.3 Malignancies including Breast Cancer

Malignancies are considered a potential risk with ocrelizumab due to the potential decreased immune surveillance associated with B-cell depletion in the context of treatments that are used long-term to treat chronic diseases. During the controlled treatment period, the incidence rate of malignancies in the ocrelizumab treatment groups across the MS program was higher than IFN or placebo groups with overlapping confidence intervals. The incidence rates were within the expected ranges for the MS population from epidemiology sources. The only cluster identified was for breast cancer. No firm conclusion can be made to date concerning the risk due to the low number and the limited follow-up; hence, the risk remains potential to date.

5.1.1.2.4 Neutropenia

In the controlled treatment period, decreased neutrophils were observed in 12% and 15% of MS patients treated with ocrelizumab in PPMS and RMS, respectively. Most were mild to moderate in severity, and approximately 1% of the patients had Grade 3 or 4 neutropenia; and no temporal association with infections was identified.

Detailed information for all risks can be found in the current Ocrelizumab Investigator's Brochure.

5.1.2 Management of Patients Who Experience Specific Adverse Events

Guidelines for management of specific adverse events are outlined in [Table 4](#). Additional guidelines are provided in the subsections below.

Table 4 Guidelines for Management of Specific Adverse Events

Event	Action to Be Taken
Mild to moderate IRR	
• If the event that a patient experiences is a mild to moderate IRR (e.g. headache), the infusion rate should be reduced to half the rate at the time of the event.• This reduced rate should be maintained for at least 30 minutes. If tolerated, the infusion rate may then be increased according to the patient's initial infusion schedule.
Severe IRR (or complex of flushing, fever, and throat pain)	
• If a patient experiences a severe IRR or a complex of flushing, fever, and throat pain symptoms, the infusion should be interrupted immediately and the patient should receive symptomatic treatment.• The infusion should be restarted only after all symptoms have resolved.• The initial infusion rate at restart should be half of the infusion rate at the time of onset of the reaction.

Table 4 Guidelines for Management of Specific Adverse Events (cont.)

Life-threatening or disabling IRR (e.g., anaphylaxis)	
• Immediately stop ocrelizumab if there are signs of a life-threatening or disabling IRR during an infusion, such as acute hypersensitivity or acute respiratory distress syndrome.• The patient should receive appropriate treatment.• Permanently discontinue ocrelizumab in these patients.
---	--

IRR=infusion-related reaction.

5.2 SAFETY PARAMETERS AND DEFINITIONS

Safety assessments will consist of monitoring and recording adverse events, including serious adverse events and adverse events of special interest, performing protocol-specified safety laboratory assessments, measuring protocol-specified vital signs, and conducting other protocol-specified tests that are deemed critical to the safety evaluation of the study.

Certain types of events require immediate reporting to the Sponsor, as outlined in Section 5.4.

5.2.1 Adverse Events

According to the ICH guideline for Good Clinical Practice, an adverse event is any untoward medical occurrence in a clinical investigation subject administered a pharmaceutical product, regardless of causal attribution. An adverse event can therefore be any of the following:

- Any unfavorable and unintended sign (including an abnormal laboratory finding), symptom, or disease temporally associated with the use of a medicinal product, whether or not considered related to the medicinal product
- Any new disease or exacerbation of an existing disease (a worsening in the character, frequency, or severity of a known condition), except as described in Section 5.3.5.10
- Recurrence of an intermittent medical condition (e.g., headache) not present at baseline
- Any deterioration in a laboratory value or other clinical test (e.g., ECG, X-ray) that is associated with symptoms or leads to a change in study treatment or concomitant treatment or discontinuation from study drug
- Adverse events that are related to a protocol-mandated intervention, including those that occur prior to assignment of study treatment (e.g., screening invasive procedures such as lumbar puncture)

5.2.2 Serious Adverse Events (Immediately Reportable to the Sponsor)

A serious adverse event is any adverse event that meets any of the following criteria:

- Is fatal (i.e., the adverse event actually causes or leads to death)
- Is life threatening (i.e., the adverse event, in the view of the investigator, places the patient at immediate risk of death)
 - This does not include any adverse event that had it occurred in a more severe form or was allowed to continue might have caused death.
- Requires or prolongs inpatient hospitalization (see Section [5.3.5.11](#))
- Results in persistent or significant disability/incapacity (i.e., the adverse event results in substantial disruption of the patient's ability to conduct normal life functions)
- Is a congenital anomaly/birth defect in a neonate/infant born to a mother exposed to study drug
- Is a significant medical event in the investigator's judgment (e.g., may jeopardize the patient or may require medical/surgical intervention to prevent one of the outcomes listed above)

The terms "severe" and "serious" are not synonymous. Severity refers to the intensity of an adverse event (e.g., rated as mild, moderate, or severe, or according to NCI CTCAE; see Section [5.3.3](#)); the event itself may be of relatively minor medical significance (such as severe headache without any further findings).

Severity and seriousness need to be independently assessed for each adverse event recorded on the eCRF.

Serious adverse events are required to be reported by the investigator to the Sponsor immediately (i.e., no more than 24 hours after learning of the event; see Section [5.4.2](#) for reporting instructions).

5.2.3 Adverse Events of Special Interest (Immediately Reportable to the Sponsor)

Adverse events of special interest are required to be reported by the investigator to the Sponsor immediately (i.e., no more than 24 hours after learning of the event; see Section [5.4.2](#) for reporting instructions). Standard adverse events of special interest include the following:

- Cases of potential drug-induced liver injury that include an elevated ALT or AST in combination with either an elevated bilirubin or clinical jaundice, as defined by Hy's law (see Section [5.3.5.7](#))
- Suspected transmission of an infectious agent by the study drug, as defined below
 - Any organism, virus, or infectious particle (e.g., prion protein transmitting transmissible spongiform encephalopathy), pathogenic or non-pathogenic, is

considered an infectious agent. A transmission of an infectious agent may be suspected from clinical symptoms or laboratory findings that indicate an infection in a patient exposed to a medicinal product. This term applies only when a contamination of the study drug is suspected.

5.3 METHODS AND TIMING FOR CAPTURING AND ASSESSING SAFETY PARAMETERS

The investigator is responsible for ensuring that all adverse events (see Section 5.2.1 for definition) are recorded on the Adverse Event eCRF and reported to the Sponsor in accordance with instructions provided in this section and in Section 5.4 – Section 5.6.

For each adverse event recorded on the Adverse Event eCRF, the investigator will make an assessment of seriousness (see Section 5.2.2 for seriousness criteria), severity (see Section 5.3.3), and causality (see Section 5.3.4).

5.3.1 Adverse Event Reporting Period

Investigators will seek information on adverse events at each patient contact. All adverse events, whether reported by the patient or noted by study personnel, will be recorded in the patient's medical record and on the Adverse Event eCRF.

After informed consent has been obtained **but prior to initiation of study drug**, only serious adverse events caused by a protocol-mandated intervention (e.g., invasive procedures such as biopsies, discontinuation of medications) should be reported (see Section 5.4.2 for instructions for reporting serious adverse events).

After initiation of study drug, all adverse events will be reported for up to 48 weeks after the last dose of study drug. After this period, the investigator should report any serious adverse events that are believed to be related to prior study drug treatment (see Section 5.6).

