3. STUDY DESIGN

3.1 DESCRIPTION OF THE STUDY

This is an open-label, multicenter, biomarker study conducted at centers in multiple countries in which all eligible patients will be enrolled to a single treatment arm of ocrelizumab. *The study will include an RMS cohort and a PPMS cohort (see Table 1). The RMS cohort is the main cohort and will include the majority of study participants. The RMS cohort will be comprised of four arms, three of which will have patients randomized into one of three arms (Arms 1–3) depending on the time of their second lumbar puncture (LP). In Arm 4, treatment with ocrelizumab will be delayed for 12 weeks after the first LP. The PPMS cohort will comprise a smaller, hypothesis-generating portion of the trial, as less is known about PPMS biomarkers.*

Arm 4 will provide a control for Arm 1 of the RMS cohort. Due to the relapsing and remitting nature of RMS, some biomarkers may change due to disease course rather than based on influence of a drug treatment. Therefore, some biomarkers may “regress to the mean” across the disease course over time, and this change could then inaccurately be reported as a change due to drug treatment over time. Arm 4 will allow for an estimate of the natural variability of the disease when analyzing the other treated arms.

Male and female patients age 18–55 years with a diagnosis of RMS or PPMS in accordance with the 2010 revised McDonald criteria ([Polman et al. 2011; Appendix 7](#)) and an EDSS score of 0–5.5 points for RMS patients, or an EDSS score of 3.0–6.5 for PPMS patients, at screening will be eligible. Screening will occur over a 4-week period, after which eligible patients may begin treatment with ocrelizumab.

For patients in the RMS cohort (Arms 1–3), ocrelizumab will be administered at Week 1, Week 3, Week 24, and Week 48. The first dose will be administered as two infusions of 300 mg given on Day 1 and Day 15. The subsequent doses will be given as single 600-mg infusions.

For patients in the RMS cohort (Arm 4), after receiving two LPs at Week –12 and Week 1, the first dose of ocrelizumab will be administered as two 300-mg infusions on Week 1 (Day 1) and Week 3 (Day 15), with subsequent doses given as single 600-mg infusions at Weeks 24 and 48. The timeline for Arm 4 will continue for an extra 12 weeks to accommodate the same one-year dosing regimen.

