5. ASSESSMENT OF SAFETY

5.1 SAFETY PLAN

Ocrelizumab is currently in clinical development for the treatment of MS. Identified and potential risks associated with ocrelizumab treatment will continue to be closely monitored throughout the clinical program. Patient safety during the ocrelizumab program is ensured by targeting the most appropriate patient population, stringent safety

monitoring by the Sponsor, and protocol-specified ocrelizumab treatment interruption criteria. Patients will be evaluated clinically and with standard laboratory tests before the study and at regular intervals during the study. Safety evaluations will consist of medical interviews, recording of adverse events, physical examinations, and standard laboratory measurements. Adverse events will be graded according to National Cancer Institute Common Terminology Criteria for Adverse Events, Version 4.0 (NCI CTCAE v4.0).

Administration of ocrelizumab will be performed in a hospital or clinic environment under close supervision of the investigator or a medically qualified staff member with immediate availability of full resuscitation facilities. All adverse events and serious adverse events will be recorded during the study and for up to 48 weeks after the last dose of ocrelizumab as provided through this study. Related serious adverse events must be collected and reported regardless of the time elapsed from the last study drug administration, even if the study has been closed. If the patient is unable to return for the safety follow-up visit, the discontinuation visit information may be collected via phone call.

Safety assessments will include the incidence, nature, and severity of (serious) adverse events graded per the NCI CTCAE v4.0. Safety assessments will be conducted *for the RMS cohort Arms 1–3 per the schedule of activities in Appendix 1, for the RMS cohort Arm 4 per the schedule of activities in Appendix 2, and for the PPMS cohort per the schedule of activities in Appendix 3.*

The potential safety issues anticipated in this study, as well as measures intended to avoid or minimize these issues, are outlined in the following sections.

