5.3.5.8 Deaths

All deaths that occur during the protocol-specified adverse event reporting period (see Section [5.3.1](#)), regardless of relationship to study drug, must be recorded on the Adverse Event eCRF and immediately reported to the Sponsor (see Section [5.4.2](#)). This includes death attributed to progression of *MS*.

Death should be considered an outcome and not a distinct event. The event or condition that caused or contributed to the fatal outcome should be recorded as the single medical concept on the Adverse Event eCRF. Generally, only one such event should be reported. The term "**sudden death**" should be used only for the occurrence of an abrupt and unexpected death due to presumed cardiac causes in a patient with or without preexisting heart disease, within 1 hour after the onset of acute symptoms or, in the case of an unwitnessed death, within 24 hours after the patient was last seen alive and stable. If the cause of death is unknown and cannot be ascertained at the time of reporting, "**unexplained death**" should be recorded on the Adverse Event eCRF. If the cause of death later becomes available (e.g., after autopsy), "unexplained death" should be replaced by the established cause of death.

If the death is attributed to progression of *MS*, "MS progression" should be recorded on the Adverse Event eCRF.

Deaths that occur after the adverse event reporting period should be reported as described in Section 5.6.

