5.4.2 Reporting Requirements for Serious Adverse Events and Adverse Events of Special Interest

5.4.2.1 Events That Occur prior to Study Drug Initiation

After informed consent has been obtained but prior to initiation of study drug, only serious adverse events caused by a protocol-mandated intervention should be reported. The Serious Adverse Event/Adverse Event of Special Interest Reporting Form provided to investigators should be completed and submitted to the Sponsor or its designee immediately (i.e., no more than 24 hours after learning of the event), either by faxing or by scanning and emailing the form using the fax number or email address provided to investigators.

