- ^s Neurological examinations will be used to distinguish relapse in MS from another neurological (non-MS) disorder. Potential relapses should be recorded throughout the treatment period. Investigators will also screen patients for signs and symptoms of worsening neurologic function localized to the cerebral cortex, such as cortical symptoms/signs, behavioral and neuropsychological alteration, retrochiasmal visual defects, hemiparesis, cerebellar symptoms/signs (e.g., gait abnormalities, limb incoordination). Patients with suspected PML should be withheld from ocrelizumab treatment until PML is ruled out by complete clinical evaluation and appropriate diagnostic testing (see [Appendix 6](#)). A patient with confirmed PML should be withdrawn from the study. PML should be reported as a serious adverse event (with all available information) with immediate notification of the Medical Monitor.
- ^t If an MRI was obtained during the 4-week screening period then that MRI can be used as the baseline brain MRI and the brain MRI does not need to be repeated at pre-treatment baseline (Day 1).
- ^u Adverse events will be reported throughout the study and for up to 48 weeks after the last dose of ocrelizumab as provided through this study. If the patient is unable to return for the safety follow-up visit, the discontinuation visit information may be captured via phone call.
- ^v Medications used after treatment discontinuation should be recorded during the Safety Follow-up Period.
- ^w All patients must receive prophylactic treatment with 100 mg of methylprednisolone (or equivalent), administered by slow IV infusion, to be completed approximately 30 minutes before the start of each ocrelizumab infusion.
- ^x Ocrelizumab will be administered at Weeks 1, 3, 24, and 48. The first dose will be administered as two infusions of 300 mg given on Day 1 and Day 15. The subsequent doses will be given as single 600-mg infusions.
- ^y For patients consenting to optional RCR sampling only. Not applicable in countries not participating in RCR sampling.
- ^z For DNA collection, only a single sample is needed and will be obtained at baseline. However, if the sample collection is missed for any reason, the sample may be obtained at any subsequent visit.

Appendix 3
Schedule of Activities for the PPMS Cohort

Week	Screening ^a	Treatment Period										Unscheduled Visit (due to relapse) ^b	Early Termination Visit	Safety Follow-Up ^c
		1 (Treatment Baseline)	3	12	24	26	36	48	50	52				

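### Arm 4's 12-week pre-dose delay falls under two conflicting adverse-event rules; the narrower one (Protocol 5.3.1 and 5.4.2.1) would miss unrelated serious events and non-serious events after the first lumbar puncture

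*Protocol*

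**What the plan says.** **The narrow rule.** For the time between consent and first study drug, Protocol 5.3.1 (second paragraph) says that "only serious adverse events caused by a protocol-mandated intervention (e.g., invasive procedures such as biopsies, discontinuation of medications) should be reported". Section 5.4.2.1 repeats it: "only serious adverse events caused by a protocol-mandated intervention should be reported". Neither section mentions Arm 4.

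**The broad rule.** Section 5.1 says: "All adverse events and serious adverse events will be recorded during the study". The first paragraph of 5.3.1 says that all adverse events, however they come to light, "will be recorded in the patient's medical record and on the Adverse Event eCRF". Appendix 2, the Arm 4 schedule, marks adverse events at Screening, at Week -12 and at every later visit. Its footnote u reads: "Adverse events will be reported throughout the study and for up to 48 weeks after the last dose of ocrelizumab".

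**Where Arm 4 stands.** Section 3.1 says: "In Arm 4, treatment with ocrelizumab will be delayed for 12 weeks after the first LP". The same section gives the arm's purpose: "Arm 4 will provide a control for Arm 1 of the RMS cohort".

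**Related provisions.** Section 5.3.5.8 requires reporting of "All deaths that occur during the protocol-specified adverse event reporting period" and refers to 5.3.1 for that period. Section 2.5 lists adverse events related to biomarker sampling among the safety endpoints, with no seriousness limit. Protocol 6.5 summarises events from Day 1 treatment onward. SAP 4.6 summarises treatment-emergent events only, apart from earlier events that become more intense on treatment.

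**The concern.** A limit of this kind suits a screening period of about 4 weeks. In Arm 4 it extends over 12 weeks in which patients are enrolled, have had one study LP and are waiting for a second. Version 4 added Arm 4, and its summary of changes lists edits to 5.1 and to parts of 5.3.5 but none to 5.3.1 or 5.4.2.1. The limit may simply have been carried over.

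Two things are at stake. First, sites reading different sections could collect different events, so Arm 4 pre-dose counts would depend on the site's reading. Second, a site that follows the narrow rule has no instruction to report an unrelated hospitalised infection in the delay. Nor would it report a non-serious complication of the first LP, which is the kind of event the sample-collection objective is meant to capture.

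**Working it through.** **1. Length of the restricted interval.** Appendix 2 puts Week -12 at Day -84 and treatment baseline at Day 1. With no Day 0 that is 84 days, and 84/7 = 12.0 weeks, which reproduces the protocol's figure. The ±7-day window on Week -12 gives 11 to 13 weeks. From Screening at Day -112 the interval is 112/7 = 16 weeks, or 12 + 8 = 20 weeks if screening is extended to 8.

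**2. Patient-time.** Protocol 6.1 plans 16 Arm 4 patients (15 before inflation).
- 16 × 84/365.25 = 3.68 patient-years
- 15 × 84/365.25 = 3.45 patient-years

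**3. The same event under each rule (Arm 4, Week -12 to first dose).**

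| Event | 5.3.1 second paragraph, 5.4.2.1 | 5.1, 5.3.1 first paragraph, Appendix 2 |
|---|---|---|
| Serious, caused by a protocol-mandated intervention | Reported | Captured |
| Serious, other cause | Not reported | Captured |
| Death, other cause | Unclear: 5.3.5.8 refers back to 5.3.1 | Captured |
| Non-serious, after the first LP | Not reported | Captured |
| Non-serious, other cause | Not reported | Captured |

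Reading one side as recording and the other as reporting does not clearly reconcile them. Footnote u is itself about reporting, and the protocol uses both verbs for the same 48-week window (5.1, 5.3.1, footnote u). Such events also have no other home: 5.3.5.9 defines a preexisting condition as one present at screening, so an event starting in the delay does not qualify.

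**4. LPs affected.** Both mandatory Arm 4 LPs come before first dose (Table 1). Across the study, pre-dose mandatory LPs number 104 first LPs + 16 second LPs in Arm 4 = 120 of 2 × 104 = 208, or 58%. In the other arms the first LP precedes dosing by at most 7 business days. Only the 16 first LPs in Arm 4 are followed by 12 weeks under the restriction.

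**5. Illustrative event counts.** The documents give no event rate for patients like those in Arm 4. Assume the interferon-group figures in Protocol 1.2.1.1 (83.3% with any event and 8.7% with a serious event over 96 weeks) and a constant hazard h = -ln(1 - p)/96 per week.
- Any event: h = 1.790/96 = 0.01864. Over 12 weeks, 1 - exp(-0.2237) = 20.0%; × 16 = 3.2 patients.
- Serious event: h = 0.0910/96 = 0.000948. Over 12 weeks, 1 - exp(-0.01138) = 1.13%; × 16 = 0.18 patients.
- Range from 15 patients at 11 weeks to 16 patients at 13 weeks: any event, 15 × 18.5% = 2.8 to 16 × 21.5% = 3.4; serious, 15 × 1.04% = 0.16 to 16 × 1.22% = 0.20.

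This range reflects patient numbers and visit timing only, not uncertainty about the borrowed rates.

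**The case against.** The strongest reply is that the text is ambiguous and nothing is certain to be lost. The first paragraph of 5.3.1 sends every event to the eCRF, and the Arm 4 schedule marks adverse events at Week -12. This stands. A reader might infer that events in the delay necessarily go unreported, but the documents support only that sites could follow either rule.

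The narrow rule is also wider than procedures. It covers any protocol-mandated intervention and names stopping of medications, so a serious event blamed on the required delay might qualify. That is arguable, but a serious event with an unrelated cause still falls outside.

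On deaths, 5.3.5.8 can be read as covering the time from consent, and 5.4 requires serious events within 24 hours regardless of relation to study drug. However, both refer on to the sections in dispute (5.3.1 and 5.4.2), so the matter stays open.

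The risk most specific to delaying treatment is disease activity, and Appendix 2 captures it separately: relapse, EDSS, neurological examination and MRI at Week -12 and Week 1. This stands and limits the gap to other events.

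A reader might also infer that Arm 4 would supply a background adverse-event rate for treated patients' first 12 weeks. The documents do not support that. Arm 4 is not randomised, is recruited separately, may stay on existing therapy, and has about 16 patients. Its planned comparison with Arm 1 concerns biomarkers and efficacy. With about 0.2 patients expected to have a serious event, no usable rate would result.

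Finally, Appendices 1 and 3 carry the same clash at screening, and the SAP synopsis comes from protocol Version 5 while the protocol supplied is Version 4. Screening is shorter, normally up to 4 weeks, so Arm 4 is where the clash matters most. Whether Version 5 changed 5.3.1 cannot be seen.

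**Conclusion.** The contradiction is real in the protocol supplied. For Arm 4, the second paragraph of 5.3.1 and 5.4.2.1 cannot be followed together with 5.1, the first paragraph of 5.3.1 and Appendix 2. The likely result is inconsistent capture over 12 weeks (11 to 13 with the visit window), about 3.4 to 3.7 patient-years. The main losses under the narrow rule would be serious events with unrelated causes, arguably deaths, and non-serious events after the first LP.

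The expected numbers are small. The figures of 3.2 and 0.2 patients are illustrative: they rest on rates from interferon-treated patients given dummy infusions and on a constant hazard, and Arm 4 patients may be untreated or on other therapy. The case for a change rests on the conflict and on the sample-collection objective, not on those counts or on any comparison with treated arms. It is a correction that should be made, at low cost.

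**What to change.** **Protocol.** Reconcile 5.3.1 and 5.4.2.1 with 5.1 and Appendix 2 by stating that, in Arm 4, reporting of adverse events and serious adverse events, including deaths, starts at the Week -12 visit. Make the reference in 5.3.5.8 agree. If protocol Version 5 already does this, only the SAP change remains.

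**SAP 4.6.** Add a separate descriptive listing or table of Arm 4 events from Week -12 to first dose, with patient-time, and no comparison with the treated arms. Base it on all Arm 4 patients who attended Week -12, because the safety population in SAP 4.1.4 requires an infusion and would omit anyone who left during the delay. For delay periods already completed, list what was entered and say that capture may have differed between sites.

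**Cost.** Some protocol and SAP wording, one extra output, and slightly more site data entry for about 16 patients over 12 weeks. The eCRF exists and the visits are already marked for adverse events.
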